# 7.1.4.2 Thromboprophylaxis

It is strongly suggested that all subjects receive an anticoagulant (eg, enteric-coated aspirin at standard prophylactic dose or other anticoagulant or antiplatelet medication, such as clopidogrel bisulfate, low molecular weight heparin, or warfarin). In addition, a second thromboprophylaxis medication is strongly recommended in subjects with elevated risk of thrombosis, based on an individual benefit/risk assessment (Li et al, 2017); see Section 12.14 for more details.

Protocol Number: 20170596

**Date:** 20 May 2019 Page 55 of 132

# 7.1.4.3 Tumor Lysis Syndrome Prophylaxis

An approved uric acid-lowering agent (eg, allopurinol) in subjects at high risk for TLS due to high tumor burden may be prescribed at the investigator's discretion, according to the Kyprolis USPI. Risk factors for TLS include but are not limited to: elevated lactate dehydrogenase, beta-2 microglobulin > 5.5 mg/L, elevated uric acid, elevated circulating plasma cells, elevated serum creatinine, presence of soft tissue plasmacytomas, or international stage III disease.

Subjects at elevated risk of TLS should be hydrated with 500 mL of normal saline or equivalent IV fluid prior to and 250 mL after the first dose of carfilzomib and each subsequent dose until the investigator determines that the risk of TLS has resolved or up to the end of the first cycle.

# 7.1.4.4 Proton-pump Inhibitor

Proton-pump inhibitor (omeprazole or equivalent) is required while on dexamethasone.

# 7.1.4.5 Other Permitted Therapies

The following medications and supportive therapies are examples of support therapies that may be used during the study:

- Antifungal prophylaxis: Fluconazole 200 mg/day (minimum) or equivalent therapy is recommended, especially for patients living (coming from) areas known to have high incidence of environmental mycoses.
- Prophylaxis for Pneumocystosis jirovenci: Pneumocystis jirovenci pneumonia prophylaxis should be considered, as per institutional guidelines while on dexamethasone.
- Bone-preserving therapy: bone preserving therapy (bisphosphonate or other bone preserving therapy) is strongly recommended for all subjects with evidence of lytic destruction of bone or with osteopenia (Gralow et al, 2013; Terpos et al, 2013). Commercially available IV bisphosphonates (pamidronate and zoledronic acid) or monoclonal antibodies are preferred when available, used according to the manufacturer's recommendations, as described in the prescribing information, for subjects with osteolytic or osteopenic myelomatous bone disease. Oral bisphosphonates may be used as alternatives if IV bisphosphonates are not available at the study site. It is preferred that investigators use the same route of bisphosphonate therapy for all subjects at their sites.
- Subjects who are using bone preserving therapy when they enter the study should continue the same treatment. Subjects with evidence of lytic destruction of bone or with osteopenia who are not using bone preserving therapy at the time of enrollment should start as soon as possible during cycle 1 or 2 of treatment. Investigators should not start bone-preserving therapy during the study, unless it has been agreed with the sponsor that there is no sign of disease progression.
- Antivirals, antihypertensives, statins, and antibiotics.
- · Hyperglycemia medical management.

Protocol Number: 20170596

**Date**: 20 May 2019 Page 56 of 132

 Prevention of constipation (eg, adequate hydration, high-fiber diet, and stool softeners, if needed)

- Prophylactic antiemetics, with the exception of corticosteroids.
- Colony-stimulating factors, erythropoietin, and transfusion of platelets and RBC.
- Loperamide is recommended for the treatment of diarrhea, starting at the time of the first watery stool. The loperamide dose and regimen is according to institutional guidelines. Prophylactic loperamide is not recommended.
- Adequate hydration is recommended for prevention of myeloma-related kidney disease.

#### 7.1.5 Other Treatment Procedures

No other treatment procedures are required. Patients may receive surgery or radiation therapy as clinically indicated.

# 7.1.6 Product Complaints

A product complaint is any written, electronic or oral communication that alleges deficiencies related to the identity, quality, durability, reliability, safety, effectiveness, or performance of a drug(s) or device(s) after it is released for distribution to market or clinic by either Amgen or by distributors and partners for whom Amgen manufactures the material.

This includes any investigational/non-investigational product(s) provisioned and/or repackaged/modified by Amgen.

Any product complaint(s) associated with an investigational product(s), non-investigational product(s), or device(s) supplied by Amgen are to be reported according to the instructions provided in the IPIM.

# 7.1.7 Excluded Treatments, Medical Devices, and/or Procedures During Study Period

Concurrent therapy with a marketed or investigational anticancer therapeutic for either a palliative or therapeutic intent is excluded. Long-term corticosteroids for nonmalignant conditions (eg, asthma, inflammatory bowel disease) equivalent to a dexamethasone dose > 4.0 mg/day or prednisone > 20 mg/day are not permitted (other than as indicated in this protocol). Higher steroid doses given short term for exacerbations of nonmalignant conditions (eg, asthma flare) if medically indicated are permitted. Investigational agents are not to be used during the study. Plasmapheresis is not permitted at any time while the subject is receiving study treatment. For subjects requiring plasmapheresis while on study treatment, every attempt should be made to document disease status by IMWG criteria first. Study treatment must be discontinued.

Protocol Number: 20170596

**Date:** 20 May 2019 Page 57 of 132

The prophylactic use of myeloid growth factors is prohibited, but they may be used for management of neutropenia in accordance with American Society of Clinical Oncology Guidelines (Smith et al, 2015).

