# 3.3.3.1.12 Thrombotic Microangiopathy

The subject incidence of thrombotic microangiopathy (TMA) was 0.2% and all events were serious. Fatal outcomes have been reported with TMA. As described in the dose modification Section 7.4, carfilzomib should be held if the diagnosis is suspected. If the diagnosis is excluded, carfilzomib may be restarted based on an individual benefit-risk assessment. The safety of reinitiating carfilzomib in subjects previously experiencing TMA (including thrombotic thrombocytopenic purpura and hemolytic-uremic syndrome) is unknown.

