Posterior reversible encephalopathy syndrome: Headaches, altered mental status, seizures, visual loss, and hypertension	If PRES is suspected, hold carfilzomib. Consider evaluation with neuroradiological imaging, specifically MRI, for onset of visual or neurological symptoms suggestive of PRES. If PRES is confirmed, permanently discontinue carfilzomib. If the diagnosis of PRES is excluded, carfilzomib administration may resume at same dose, if clinically appropriate.		
Thrombotic microangiopathy: Fever, microangiopathic hemolytic anemia, renal failure, thrombocytopenia, neurological manifestations	If the diagnosis is suspected, hold carfilzomib and manage per standard of care including plasma exchange as clinically appropriate. If TMA is confirmed, permanently discontinue carfilzomib. If the diagnosis is excluded, carfilzomib can be restarted at prior dose		

Page 2 of 3

Footnotes defined on last page of this table.

Protocol Number: 20170596

**Date:** 20 May 2019 Page 62 of 132

Table 7-4. Dose Modification Guidelines for Nonhematologic Toxicities

For grading criteria, see CTCAE grading scale in Section 12.4.		
Symptom/Sign/Investigation	Recommended Action	
Venous thrombosis (≥ grade 3)	Hold carfilzomib and adjust anticoagulation regimen; resume at full dose once anticoagulation has been optimized per treating investigator's discretion.	
Any other drug-related nonhematologic toxicity ≥ grade 3 b	For carfilzomib attribution, hold dose. Resume at 1 dose decrement when toxicity has resolved to grade 1 or less or to baseline grade.	

Page 3 of 3

ALT = alanine aminotransferase; ANC = absolute neutrophil count; ARDS = acute respiratory distress syndrome; AST = aspartate aminotransferase; CTCAE = Common Terminology Criteria for Adverse Events; DBP = diastolic blood pressure; GFR = Glomerular Filtration Rate; LDH = lactate dehydrogenase; MRI = magnetic resonance imaging; NCI-CTCAE = National Cancer Institute-Common Terminology Criteria for Adverse Events; PRES = Posterior Reversible Encephalopathy Syndrome; SBP = systolic blood pressure; TMA = thrombotic microangiopathy; ULN = upper limit of normal.

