Progression-free survival will be right-censored for subjects who met one of the following conditions: 1) no baseline disease assessments, 2) non-protocol anti-myeloma therapy started before documentation of disease progression or death, 3) death or disease progression immediately after more than 1 consecutively missed disease assessment visit, or 4) alive and does not have documentation of disease progression before a data analysis cutoff date. These conventions are based on the May 2007 FDA Guidance for Industry, 'Clinical Trial Endpoints for the Approval of Cancer Drugs and Biologics' (https://www.fda.gov/downloads/Drugs/Guidances/ucm071590.pdf), The censoring rules for the primary analysis of PFS are described in Table 5-1. Additionally, if the last disease assessment date is after the date that triggers the analysis, the subject will be censored at the analysis trigger date.

Date: 08 June 2018 Page 13 of 27

Table 5-1 Conventions for Censoring for PD dates

	Date of Progression or	
Situation	Censoring	Outcome
No baseline disease assessments	Date of first dose	Censored
New anti-myeloma therapy started	Date of last disease assessment	Censored
before documentation of PD	prior to start of new	
or death	anti-myeloma therapy	
Death or PD immediately after	Date of last disease assessment	Censored
more than 1 consecutively	visit without documentation of PD	
missed disease assessment visit	that is before the first missed visit	
Alive and without PD	Date of last disease assessment	Censored
documentation (including lost to		
follow-up without PD)		
Death or PD between planned	Date of death or first disease	Progressed
disease assessments	assessment showing PD,	
	whichever occurs first	
Death before first disease	Date of death	Progressed
assessment		

Treatment-emergent Adverse Event

AEs starting on or after first dose of investigational product as indicated by field "*Did* event start before first dose of investigational product?" in Events page and up to 30 days, inclusive, after the last dose of study treatment.

6. Analysis Sets

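### Section 7.1.7 ends study treatment for any subject who needs plasmapheresis, but Table 7-4 lets carfilzomib restart after plasma exchange for suspected thrombotic microangiopathy that is then excluded

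*Protocol*

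**What the plan says.** Protocol Section 7.1.7 lists treatments excluded during the study. On plasmapheresis it says "Plasmapheresis is not permitted at any time while the subject is receiving study treatment". For a subject who needs it, sites should try to document disease status by IMWG criteria beforehand, and then "Study treatment must be discontinued". No indication is exempted.

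The TMA row of Table 7-4 gives a different course. On suspicion, the site is to "hold carfilzomib and manage per standard of care including plasma exchange as clinically appropriate". If TMA is confirmed, carfilzomib stops permanently. If not, the row says "If the diagnosis is excluded, carfilzomib can be restarted at prior dose". It mentions neither the other study drugs nor documentation of disease status before the exchange.

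Section 3.3.3.1.12 also holds carfilzomib on suspicion and allows a return: "If the diagnosis is excluded, carfilzomib may be restarted based on an individual benefit-risk assessment". It does not mention plasma exchange.

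**The concern.** A site working up suspected TMA may have to decide on plasma exchange quickly. Under Table 7-4 it may exchange and, if TMA is excluded, resume carfilzomib. Under Section 7.1.7 the need for the exchange already ends study treatment. Two sites could treat the same case in opposite ways, and each could cite the protocol.

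The choice carries into the primary endpoints. A subject whose treatment ends cannot complete 12 cycles, while a subject who restarts still can. The share of the intended cumulative dose, the relative dose intensity and the recorded reasons for modification or discontinuation change with it. Differences between sites in these measures would then partly reflect which section was followed, in a study meant to describe tolerability and adherence.

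**Working it through.** **1. The plan's own precision figure (not in dispute; it sets the scale).** Protocol Section 10.1 gives 95% CI half-widths for 12-cycle completion of 20.5, 18.1 and 13.5 points at 50%, 75% and 90% with n = 25. The Clopper-Pearson limits are L = Beta(0.025; x, n − x + 1) and U = Beta(0.975; x + 1, n − x). With x = np and half-width (U − L)/2, they give 20.46, 18.09 and 13.49, which matches.

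**2. The two rules side by side.**

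| Situation | Section 7.1.7 | Table 7-4, TMA row | Compatible? |
|---|---|---|---|
| TMA suspected, no exchange | Does not apply | Hold carfilzomib, then follow the diagnosis | Yes |
| TMA suspected, exchange needed | Barred on study treatment; study treatment ends | Carfilzomib held; exchange allowed; other drugs not mentioned | No |
| Exchanged, TMA then excluded | Study treatment already ended; no return described | Carfilzomib may restart at the prior dose | No |
| Exchanged, TMA confirmed | All study treatment ends | Carfilzomib ends; other drugs not mentioned | For carfilzomib only |

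The direct contradiction is confined to subjects who are exchanged on suspicion and then cleared. In the confirmed case, what is unresolved is dexamethasone, lenalidomide and pomalidomide.

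**3. Effect of one subject on the endpoints.**
- Completion: 1/25 = 4.0 points. For example, 18/25 is 72% (95% CI 50.6 to 87.9) and 19/25 is 76% (54.9 to 90.6).
- Share of full intended cumulative dose, Kd arm, from Section 7.1.1.2. Cycle 1 is 2×20 + 4×56 = 264, cycle 2 is 6×56 = 336, and cycles 3 to 12 are 10×3×70 = 2100, for a total of 2700 mg/m². As an illustration, take a subject fully dosed through cycle 4, who has received 264 + 336 + 2×210 = 1020.
  - Stopped there: 1020/2700 = 37.8%.
  - Restarted after missing one 70 mg/m² dose and then fully dosed: 2630/2700 = 97.4%.
  - Shift in the arm mean: (97.4 − 37.8)/25 = 2.4 points.

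**4. Frequency.** Section 3.3.3.1.12 gives a TMA incidence of 0.2%.
- Expected among 75: 0.002 × 75 = 0.15.
- P(at least one) = 1 − 0.998^75 = 13.9%; for one arm of 25, 1 − 0.998^25 = 4.9%.

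These are confirmed cases, whereas the direct contradiction concerns excluded ones, for which the documents give no rate. If suspicion arose in 1% to 5% of subjects (an assumption without a source), 0.75 to 3.75 of 75 would be suspected. Only those who were also exchanged and then cleared would meet the contradiction, so this is a ceiling under that assumption and not an estimate.

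**The case against.** **A subject on hold is not receiving study treatment.** Section 7.4.1.1 counts a subject as on protocol treatment while receiving carfilzomib, so an exchange during a hold might fall outside the bar. This does not remove the conflict. Section 7 defines study treatment to include the non-investigational products, the TMA row holds carfilzomib only, and status during a hold is not stated. Section 7.1.7 also calls for discontinuation, which is more than a hold.

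**Table 7-4 is only guidance.** Its column is headed as a recommended action. But Section 7.4.1.1 makes carfilzomib dose modification according to Tables 7-3 and 7-4 mandatory.

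**The two sections address different procedures.** The IMWG step in 7.1.7 suggests that its authors had plasmapheresis for the myeloma in mind. That may well be the intent, but the text draws no line by indication.

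**The event is rare.** This stands, and it limits the size of the point.

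Some stronger inferences are not supported:
- *The other study drugs continue during the exchange.* The row is silent on them, and Sections 7.4.1.4 and 7.4.1.5 let the investigator delay or stop lenalidomide or pomalidomide for treatment-related toxicity.
- *Suspicion will be common, because thrombocytopenia (33.8%) and acute renal failure (10.8%) are common.* Table 7-4 lists these among the features of a syndrome. Their separate rates do not show how often TMA is suspected.
- *Section 7.1.5 contradicts 7.1.7 on radiation.* The former says "Patients may receive surgery or radiation therapy as clinically indicated"; the latter says an "anticancer therapeutic for either a palliative or therapeutic intent is excluded". Exclusion criteria 220 and 222 use that term for drug therapy and list radiation separately, so the two sections are compatible.
- *Radiation escapes PFS censoring because the SAP definition speaks of* "non-protocol anti-myeloma therapy started before documentation of disease progression or death". SAP Table 5-1 censors for new anti-myeloma therapy without that qualifier. What remains is an undefined term.
- *Shrinkage of an irradiated plasmacytoma can by itself produce a response.* Protocol Section 12.8 requires plasmacytoma reduction in addition to the M-protein or free light chain criteria.
- *Response and PFS follow conflicting rules and are biased upward.* Only continuation of treatment faces two rules. Disease assessment goes on after treatment stops, up to 12 months from enrollment (Section 9.2.2), and no bias has been shown.

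**Conclusion.** The conflict on plasma exchange holds. A subject exchanged for suspected TMA and later cleared must stop all study treatment under Section 7.1.7 and may restart carfilzomib under Table 7-4. When TMA is confirmed, the sections agree on carfilzomib and leave the other study drugs unresolved. One affected subject moves completion by 4 points in an arm of 25, which is small beside the planned half-widths of 13.5 to 20.5 points. Most likely very few subjects, possibly none, will be affected, but their number cannot be estimated from the documents. The point deserves correction because sites would face contradictory instructions in an urgent work-up and because a primary endpoint depends on which is followed.

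This assumes that plasmapheresis in 7.1.7 covers plasma exchange as used in Table 7-4; neither term is defined.

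**What to change.** Reconcile the plasmapheresis sentences of Section 7.1.7 with the TMA row of Table 7-4 and with Section 3.3.3.1.12. One instruction should cover plasma exchange for suspected TMA, both when the diagnosis is excluded and when it is confirmed, for carfilzomib and for each of the other study drugs. It should also say whether disease status must be documented before the exchange, and the restart wording of Table 7-4 and Section 3.3.3.1.12 should be aligned. Which rule applies is for the sponsor to decide.

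The cost is wording in up to three places in the protocol, through an amendment. No sample size, visit or analysis changes.

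Separately, the SAP is dated 08 June 2018 and cites the 06 March 2018 protocol. When it is updated, it can state whether radiation to a myeloma lesion counts as new anti-myeloma therapy. That is a routine definition and not part of this conflict.

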# 7.2 Method of Treatment Assignment

Subjects who meet eligibility criteria will be assigned by the investigator to treatment with either Kd, KRd, or KPd; no cross-over will be allowed.

Investigators are advised to consider the following guidelines when assigning subjects to treatment:

- Kd arm: it is recommended that subjects who are suitable for an IMid free doublet regimen are assigned to the Kd arm.
- KRd arm: it is recommended that subjects who are not refractory to lenalidomide (lenalidomide sensitive or naïve) and who are suitable for triplet therapy are assigned to the KRd arm.
- KPd arm: it is recommended that subjects who are refractory to lenalidomide (progressed on or within 60 days of completing this therapy) and who are suitable for a triplet therapy are assigned to the KPd arm.

The treatment assignment date is to be documented in the subject's medical record and on the enrollment CRF.

# 7.3 Blinding

This is an open-label study; blinding procedures are not applicable.

#### 7.4 Dose Modification

# 7.4.1 Dosage Adjustments, Delays, Rules for Withholding or Restarting, Permanent Discontinuation

# 7.4.1.1 Amgen Investigational Product: Carfilzomib

The reason for dose change of carfilzomib is to be recorded on each subject's CRF.

Carfilzomib may be discontinued, temporarily delayed, or dosage temporarily reduced, in the event of a treatment-related toxicity that, in the opinion of the investigator, warrants the discontinuation, temporary delay or dose reduction. Carfilzomib dose must be modified based on specified toxicities, as indicated in Table 7-3 and Table 7-4. The subject will be considered on protocol treatment while receiving carfilzomib. Carfilzomib (both twice-weekly and once-weekly regimen) must be discontinued permanently if a delay of more than 6 weeks is required due to unresolved toxicity.

If day 1 of a cycle is delayed, day 1 of subsequent cycles should be adjusted accordingly to maintain the 28-day cycle duration. However, if a within-cycle dose is delayed, then the dates of the subsequent within-cycle doses should not be adjusted.

Protocol Number: 20170596

**Date**: 20 May 2019 Page 58 of 132

If carfilzomib administration does not commence within the allowable window of the scheduled administration date, then the dose will be considered a missed dose. Administration may resume at the next planned dosing date. A missed dose will not be made up.

If either carfilzomib or dexamethasone are held for the remainder of the previous cycle or the new cycle is delayed due to residual toxicity on the planned day 1 of the next cycle, then the new cycle will be started at 1 dose decrement for the drug(s) causing the delay.

For conditions that do not require carfilzomib dose reduction, refer to Section 7.4.1.3.

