**Protocol Number: 20170596** 

**Date:** 20 May 2019 **Page 19 of 132** 

Table 2-1. Schedule of Activities

			1	ıa	bie	Z- I	. 3	CII	euu	ne e	UI F	1 Cu	viu	es	1		
			Screening a b (up to						nt F	Peri	od				Safety FU°		
			21 days before		1	Cyc	le 1	 -2				Су	cle	3-12	(30 [+3] days post		
PROCEDU	RE		Day 1)	Day 1	2	8	9	15	16	22	23	1	8	15 21		Notes	
Concomita	nt thera	pies review					Сс	ntir	านอน	IS							
LABORAT		SSESSMENTS															
	Kd Arm	Urine or serum	X	Х								Х			Х		
		Serum	X												Χ		
		Urine or serum cycle 1 (predose)		Х		х		X		Х							
Pregnancy test (FCBP only) d	and KRd	Urine or serum cycle 2 to 12 (predose; regular menses)		х								х				Within 24 hours prior to dose of lenalidomide or pomalidomide for subjects in the KRd or KRd or a respectively.	
	Arms	Urine or serum cycle 2 to 12 (predose; irregular menses)		Х				X				X		Х		in the KRd or KPd arms, respectively	
Hematology	у	, ,	х	Х								Х			Х	Hematology and chemistry samples from screening may be used for C1D1 if taken within 3 days prior to C1D1. Lab	
Chemistry			Х	×								X			X	results must be evaluated for potential dose modification assessment prior to dosing (see Section 7.4). Chemistry and hematology assessments, other than for C1D1, may be taken within 2 days prior to the scheduled assessment.	

Page 2 of 7

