#### 3.3.3.1.9 Hemorrhage and Thrombocytopenia

The subject incidence of hemorrhage and thrombocytopenia was 19.5% and 33.8%, respectively. The subject incidence of serious hemorrhage and serious thrombocytopenia was 2.2% and 1.5%, respectively. Thrombocytopenia is a significant risk factor for hemorrhage events. Fatal outcomes have been reported for these events. Carfilzomib causes thrombocytopenia with platelet nadirs observed between day 8 and 15 of each 28-day cycle with recovery to baseline platelet count by the start of the next cycle. Serial monitoring of platelets will be performed every 28 days throughout treatment period (see Schedule of Activities, Table 2-1). Dose modification guidance for thrombocytopenia (including stopping carfilzomib) is provided in Section 7.4.

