#### 7.4.1.1.1 Dose Reduction Levels

Dose reduction levels of carfilzomib for toxicity management of individual subjects are provided in Table 7-2. Subjects that require dose reduction may have the dose escalated according to specific rules, see Section 7.4.1.1.4. Subjects should have the starting nominal dose of carfilzomib (56 mg/m² or 70 mg/m² based on treatment arm) on day 1 cycle 3 reduced by the same number of dose levels and the same percentage dose reduction as they were reduced during cycle 2, see Table 7-2 for dose level reductions. Subjects who require fifth dose reductions should discontinue carfilzomib.

Table 7-2. Dose Decrements for Carfilzomib

Nominal	First Dose Reduction	Second Dose Reduction	Third Dose Reduction	Fourth Dose Reduction
Dose a, b	Dose -1	Dose -2	Dose -3	Dose -4
(mg/m  )	(mg/m²)	(mg/m²)	(mg/m²)	(mg/m²)
20	15	11	Discontinue	
27	20	15	11	Discontinue
56	45	36	27	20
70	56	45	36	27

<sup>a If dose reduction of carfilzomib is required on Cycle 1 Day 1 or Cycle 1 Day 2 for any reason other than mild hepatic insufficiency, the investigator should contact the medical monitor to discuss the situation, before any additional doses of carfilzomib are administered.

<sup>b For patients with baseline chronic hepatic impairment (mild), reduce the starting and subsequent doses of carfilzomib by 25% (ie, 15 mg/m² day 1 and 2 of cycle 1 and 42 mg/m² day 8 cycle 1 and thereafter).

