**Protocol Number: 20170596** 

**Date:** 20 May 2019 Page **59 of 132** 

# 7.4.1.1.2 Guidelines for Hematologic Toxicity

Guidelines for carfilzomib dose modification in the event of thrombocytopenia and neutropenia are summarized in Table 7-3.

Table 7-3. Dose Modification Guidelines for Thrombocytopenia and Neutropenia

Hematologic toxicity	Recommended Action		
Thrombocytopenia			
When platelets fall to < 30 x 10  /L and for each subsequent drop to < 30 x 10  /L  Neutropenia	If platelets 10 to 30 x 109/L without evidence of bleeding	
 
hold
 
restart at previous dose when platelets > 30 x 10^9/L
 
	
	If evidence of bleeding or platelets < 10 x 10  /L	
 
hold
 
restart at 1 dose decrement when platelets > 30 x 10^9/L
 
	
When ANC falls to < 0.75 x 10  /L and for each subsequent drop to < 0.75 x 10  /L	If ANC 0.5 to 0.75 x 109/L	continue at full dose	
	If ANC < 0.5 x 10  /L	
 
hold dose
 
resume at 1 dose decrement when ANC ≥ 0.5 x 10^9/L
 
	

ANC = absolute neutrophil count.

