# 7.4.1.1.4 Rules for Re-escalation of Carfilzomib Dose Following Toxicity

Conditions of carfilzomib-related toxicity that are not permitted for dose re-escalation:

- Pulmonary hypertension
- Non-infectious pulmonary toxicities (per Table 7-4)
- Congestive heart failure (≥ grade 3)

A reduction in dose level required for any of the adverse events listed above may not be re-escalated. For all other carfilzomib-related toxicities that require dose level reduction, if the reduced dose level is tolerated for 1 full cycle, carfilzomib may be re-escalated at the treating physician's discretion up to the maximum dose planned in that cycle (56 mg/m² twice weekly or 70 mg/m² once weekly).

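### When platelets of 10-30 x 10^9/L without bleeding delay day 1 of a carfilzomib cycle, the protocol gives two restart doses and does not say which prevails (minor)

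*Protocol*

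**What the plan says.** Protocol Section 7.4.1.1 contains both instructions.

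- **Delayed-cycle rule.** One of its triggers is that "the new cycle is delayed due to residual toxicity on the planned day 1 of the next cycle". The consequence is that "then the new cycle will be started at 1 dose decrement for the drug(s) causing the delay". No toxicity is exempted.
- **Table rule.** "Carfilzomib dose must be modified based on specified toxicities, as indicated in Table 7-3 and Table 7-4". In Table 7-3, the row for platelets of 10-30 x 10^9/L without bleeding says to hold, then "restart at previous dose when platelets" exceed 30 x 10^9/L. The table keeps the one-level decrement for bleeding or platelets below 10 x 10^9/L. It does not separate holds within a cycle from holds at day 1.

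Table 2-1 schedules on-treatment hematology on day 1 of each cycle and requires the result to be assessed against Section 7.4 before dosing.

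Section 10.3.2.3.1 makes dose reductions, withheld doses and dose delays, with reasons, part of the primary analysis in all three arms, along with relative dose intensity and the proportion of intended cumulative dose received.

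**The concern.** Two sites can each follow a written rule and give the same kind of patient doses one level apart. Both would record a dose delay, but only the site applying the decrement would also record a dose reduction. The study exists to describe tolerability and adherence. Whether a subject counts as dose-reduced should therefore reflect tolerability, not which of two sentences the site read first.

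**Working it through.** **Step 1. Do both rules reach the same event?** Take a count of 10-30 x 10^9/L without bleeding on planned day 1, attributed to carfilzomib.

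- *Recovery within 2 days.* Section 7.1.1.2 allows dosing on the scheduled day +/- 2 days. The dose is in window, so the cycle need not count as delayed and Table 7-3 alone applies.
- *No recovery in the window, dose treated as missed.* Section 7.4.1.1 lets dosing resume at the next planned date. Day 1 need not move, so again there is no delayed cycle.
- *No recovery in the window, day 1 moved.* Section 7.4.1.1 provides for this by shifting day 1 of later cycles. The cycle is now delayed by a toxicity that has persisted. The delayed-cycle rule requires one decrement and Table 7-3 requires the previous dose.

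The conflict is confined to the third case.

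**Step 2. Does any text rank the rules?**

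- The sentence making the tables mandatory binds sites to them but does not place them above the delayed-cycle rule, which is equally directive. The table's own column is headed as recommended action.
- Section 7.4.1.3, the cross-reference that follows the delayed-cycle rule, does not list thrombocytopenia.
- Section 7.4.1.1.4 applies only after a reduction: "if the reduced dose level is tolerated for 1 full cycle, carfilzomib may be re-escalated".
- The SAP does not address restart dose. It was also written for the earlier Kd-only protocol.

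**Step 3. Dose difference (Tables 7-1 and 7-2).**

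| Setting | Table 7-3 | Section 7.4.1.1 | Difference |
|---|---|---|---|
| Kd, cycles 3-12 | 70 | 56 | 14/70 = 20.0% |
| Kd, cycle 2; KRd/KPd, cycles 3-12 | 56 | 45 | 11/56 = 19.6% |
| KRd/KPd, cycle 2 | 27 | 20 | 7/27 = 25.9% |

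**Step 4. Share of planned cumulative carfilzomib for one affected subject.**

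Planned dose (mg/m2):
- Kd: 2x20 + 4x56 + 6x56 + 30x70 = 2700
- KRd/KPd: 2x20 + 4x27 + 6x27 + 30x56 = 1990

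The delay occurs under either rule and cancels. Section 7.4.1.1.1 carries a cycle 2 reduction forward: the cycle 3 starting dose is "reduced by the same number of dose levels and the same percentage dose reduction as they were reduced during cycle 2".

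| Decrement lasts | Kd | KRd/KPd | Shift in a 25-subject arm mean (share/25) |
|---|---|---|---|
| One once-weekly cycle | 3x14 = 42 (1.56%) | 3x11 = 33 (1.66%) | 0.06; 0.07 points |
| Cycle 2 only | 6x11 = 66 (2.44%) | 6x7 = 42 (2.11%) | 0.10; 0.08 points |
| Cycles 2 and 3 | 66+42 = 108 (4.00%) | 42+33 = 75 (3.77%) | 0.16; 0.15 points |
| Cycles 4-12, never re-escalated | 9x42 = 378 (14.0%) | 9x33 = 297 (14.9%) | 0.56; 0.60 points |

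**Step 5. Scale.** The planned 95% half-width for mean relative dose intensity is 1.96 x SD/sqrt(25). For SD 5, 10 and 15 this gives 2.0, 3.9 and 5.9 points, matching Section 10.1. Every shift in Step 4 is well below the smallest of these.

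For the dose-reduced proportion, one subject is 1/25 = 4 points. Section 10.1 states half-widths of 13.5 points at 10% and 20.5 at 50%. The 4 points apply only if the subject has no other reduction; otherwise the shift is zero.

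**The case against.** The strongest answer is that the rules complement each other: Table 7-3 handles a fall in platelets, and the decrement handles failure to recover by the next cycle. Section 3.3.3.1.9 fits this, since it places the nadir between days 8 and 15 with "recovery to baseline platelet count by the start of the next cycle". An opposite reading is also available: the toxicity-specific table, being mandatory, overrides the general sentence. Each is reasonable and neither is written. They lead to different doses, so the availability of both does not remove the problem.

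Other objections narrow the point, and they stand. The dosing window and the missed-dose rule take out many low day-1 counts. Whether a drop first found on day 1 is residual toxicity is arguable. In KRd and KPd, attribution to carfilzomib competes with lenalidomide or pomalidomide, which have their own modification sections. Section 7.4.1.1 also lets the investigator reduce the dose for a treatment-related toxicity on judgment, so clearer text would not make practice fully uniform. The reason for each dose change is recorded and reported.

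A reader might infer that any platelet count of 10-30 x 10^9/L on day 1 triggers both rules. Step 1 shows that it does not: the cycle must actually be delayed.

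**Conclusion.** A minor point, but the text is wrong as written. In the narrow case of a day 1 actually delayed by carfilzomib-attributed platelets of 10-30 x 10^9/L without bleeding, two stated rules give doses one level apart and no text ranks them. The visible effect is on the dose-reduced classification, by 4 points of an arm per affected subject with no other reduction. The effect on mean relative dose intensity is negligible.

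The Step 4 figures assume a single decrement in a subject otherwise planned for 12 full cycles. Frequency is not assumed. The documents do not give the rate of this platelet band persisting past day 1, and the expected recovery by the next cycle suggests it is low.

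A reader might also infer a safety problem or a compromised primary analysis. The documents support neither: both doses are permitted levels in Table 7-2, and the study is descriptive with no threshold tested.

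**What to change.** Add to the delayed-cycle sentence in Section 7.4.1.1: *except where Table 7-3 or Table 7-4 specifies restart at the previous, same or full dose*. Naming Table 7-4 covers its rows with the same kind of restart instruction, where the same conflict could arise if carfilzomib is the drug causing the delay.

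If the sponsor intends the decrement at a cycle boundary, write it into those table rows instead: *if the hold delays day 1 of the next cycle, restart at 1 dose decrement*. The choice belongs to the sponsor's clinical team.

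The cost is one sentence in an amendment or dosing memo. Amendment 4 was issued for dosing corrections of similar size. The case report form already captures the reason for a dose change, so no new data field is needed.
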